In addition to exercise performed as part of a structured training program, physical activity behaviors are important determinants of physical and mental health. Greater total physical activity levels are associated with increased physical function, improved mental health, increased energy and decreased symptoms of chronic pain. To our knowledge, none of the exercise training trials in FM have actually measured the impact of the exercise training on physical activity behaviors during daytime hours outside the intervention. It is plausible that the adoption of a structured exercise training program reduces physical activities performed during the rest of the day, and that this change in total physical activity could affect health outcomes. Objective measurement of physical activity will allow us to determine whether RET increases, decreases or has no impact on total physical activity levels in GV's with CMP. This will allow us to begin to characterize sub-groups who benefit the most from RET (e.g. potentially those GV's that maintain or increase their extra-intervention physical activity). Thus, in addition to supervised RET, we will objectively measure total physical activity levels outside of the intervention using accelerometers before, during and following treatment.

In summary, we propose to determine the efficacy of RET for the treatment of CMP and associated symptoms in GV's. In addition, we will assess the influence of RET on total physical activity, pain sensitivity and regulation, and brain white matter tracts. By applying functional neuroimaging techniques in conjunction with pain psychophysics we will test how the brains of Veterans with CMP respond to sensory stimuli and whether these responses can be modified by exercise training. We plan to use blood oxygen level dependent (BOLD)

and diffusion tensor imaging (DTI) methods to evaluate the function of brain regions involved in pain processing and control and the microstructural properties of white matter tract pathways that connect these regions. In addition, we will determine the influence of RET on extra-intervention physical activity behaviors, testing a critical and unanswered question - whether total physical activity levels change as a result of engaging in a RET program in patients with CMP. The primary goals of this project will be accomplished by comparing GV's with CMP assigned to either RET or wait-list control (WLC) in a randomized controlled trial.

Background and Significance

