Hypothesis 1: GV's with CMP assigned to RET will show statistically significant and clinically meaningful improvements in self-reported pain, physical function and PGIC compared to WLC. We also expect significant improvements in the secondary outcomes known to change after exercise training (e.g. sleep, self-esteem, fatigue, anxiety and depression).

Aim2: To determine the influence of RET on total daily physical activity levels using complementary subjective self report and objective measures (accelerometers).

Hypothesis 2: GV's with CMP assigned to RET will show an increase in total physical activity by the end of the trial that is attributable entirely to an increase in RET.

Aim 3: To determine the influence of RET on brain mechanisms of pain **sensitivity** and **regulation** in GV's with CMP compared to WLC. Brain responses to painful heat stimuli will be measured using fMRI. Pain sensitivity will be determined by exposing participants to mild, moderate and strong pain stimuli. Pain regulation will be determined by having the participants perform attention-demanding cognitive tasks while receiving moderately painful stimuli.

Hypothesis 3A (Pain Sensitivity): GV's assigned to RET will show decreased ratings and decreased brain responses to experimental pain stimuli by the end of the treatment trial compared to baseline.

Hypothesis 3B (Pain Regulation): By the end of the treatment trial, GV's assigned to RET will show **decreased** brain responses in areas that process the sensory aspects of pain (e.g. cingulate & sensory cortices), and **increased** brain responses in areas that modulate or inhibit pain when diverting their attention away from a painful stimulus compared to baseline.

Aim 4: To determine the influence of RET on pain-relevant brain white matter tracts in GV's with CMP compared to WLC by conducting DTI analyses of white matter tracts from the thalamus to regions of the brain involved in pain processing and control (e.g. insula, periaqueductal gray, frontal and cingulate regions).

Hypothesis 4A: GV's assigned to RET will show improvements in white matter (measured as increased fractional anisotropy and/or decreased mean diffusivity) compared to baseline.

Research Design and Methods

Pilot subjects:

Five healthy adults (ages 18-60) will be recruited for a single MRI scanning session.

Screening and exclusion criteria for pilot subjects:

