The primary outcome measures to test efficacy are visual analogue scales (VAS) of pain intensity and affect of widespread muscle pain symptoms, the physical component summary (PCS) of the SF-36, and the patient global impression of change (PGIC) scale. These valid measures are widely used and recommended as core outcomes in chronic pain treatment trials (63). The primary outcome measures for Aim 2 are self-report and objectively measured estimates of total physical activity. Self-reported physical activity will be measured using the International Physical Activity Questionnaire (IPAQ). Objective estimates of physical activity will be obtained using an accelerometer during the week immediately preceding the baseline visit to the Waisman brain imaging laboratory, at weeks 5, 10 and 16 of RET or WLC and at 6- and 12-month follow-ups.

Suprathreshold pain sensitivity will be assessed using scaling procedures as described by Gracely and colleagues (64). For painful heat stimuli, subjects will be randomly presented one of three stimuli (45°C, 47°C,

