Our experience and data in CMP patients show that MRI habituation procedures are effective to screen for claustrophobia, deliver relative pain stimuli, enhance task performance and minimize subject motion. MRI habituation will take place in the MRI simulator at Waisman. This will entail being placed in a mock MRI unit, trained to rate painful stimuli, and perform the cognitive tasks (Stroop) using the same equipment that will be used in the 3T MRI unit. Pain psychophysics are also conducted and used to calculate the temperature designed to elicit moderate pain ratings. We have found that by habituating subjects they report feeling more at-ease in the MRI which should enhance measurement reliability. Our motion parameters indicate that by habituating subjects' data loss due to motion artifact is limited. In our FM study, quality data analyses indicate that only 6 of 100 subjects had motion exceeding 3 mm. The mock MRI is virtually identical to the actual MRI including fed-in scanner noise. Subjects practice with a scanner-compatible button-press response unit (Current Designs Inc., PA) while viewing stimuli through MRI compatible goggles.

Physical Activity Assessment

Baseline physical activity assessment will occur for one week prior to baseline brain imaging using an accelerometer. Physical activity will also be assessed for one week prior to each testing session. Subjects will be given instructions on the proper use of the accelerometer and will be asked to wear it as much as possible, unless sleeping, bathing or swimming, for the week preceding their baseline assessment.

Baseline Assessment and 16-Week Trial (RET vs. WLC)

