After the baseline physical activity assessment, Veterans will return for baseline brain imaging including tests of pain sensitivity and regulation and diffusion tensor imaging. As a safety precaution for pain testing during the MRI scan, all subjects will be provided with easy access to a squeeze-bulb alarm in order to interrupt a scan in progress. Subjects will be instructed to use (squeeze) the alarm trigger if they can no longer tolerate the pain stimulus or if they are too uncomfortable in the scanner to continue. Standard procedure for the MRI technicians at the Waisman lab is to immediately stop the scan if the subject triggers the alarm. Likewise, study staff will immediately stop any thermal stimulus protocol in operation should the subject trigger the alarm. If the procedures during a scanning session are interrupted due to an equipment failure, we will end the session and ask the participant to reschedule. Subjects will be paid \$75 and have travel reimbursed for any session ended prematurely for any reason.

Once the first twelve Veterans are screened, baseline tested and assigned to groups we will begin the first 16 weeks of RET and WLC. During RET and WLC protocols, Veterans will be scheduled to return to the Waisman center on weeks 6, 11 and 17 for retesting of the primary and secondary outcomes. The testing will be conducted on the non-exercise training days or prior to exercise on training days to avoid having acute exercise influence the outcomes. Physical activity assessment via accelerometry will always be collected on the week immediately preceding visit to Waisman (i.e. weeks 5, 10 and 16) so that we can determine the relationships between total physical activity, symptoms and brain function and structure. Due to the number of brain scans required, and the availability of the 3T MRI, we plan to test Veterans in small cohorts on the same day. However, should a particular participant fall out of time with their respective cohort, we will test them per the protocol (i.e. at 6, 11 and 17 weeks). During each 16-week cohort, we will be screening, clinically assessing and baseline testing the next cohort of 12 Veterans to begin their 16-week assignment. Veterans will be tested at 6 and 12 months post RET or WLC in order to obtain follow-up symptom, physical activity and brain function and structure data.

Blood Collection

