Power estimates for the trial are based on Specific Aim 1. General multivariate regression models will be used to estimate the time averaged difference in pain ratings and clinical symptom scores (continuous measurements) between the treatment and the control group. With general multivariate regression models we model both the dependence of the response on the explanatory variables as well as the autocorrelation among the responses. In order to achieve 90% power, at alpha equal to .05, with an effect size of .6 (minimum effect size of clinical importance) and with a correlation of .6 between measurements from each individual, the necessary sample size would be 34 subjects per group. If we take into account a 20% subject attrition rate, then the total sample size should be 41 subjects per group. All randomized subjects will be included in the analysis within the appropriate arm that they were randomly assigned (i.e. an intent-to-treat analysis will be used). Noncompliance, protocol deviations, withdrawal or any other problem that occur after randomization will be ignored and the participant's last observed data points will be carried forward in the analyses. Missing data will be assumed to be missing completely at random and appropriate missing data methods will be used (i.e. multiple imputation) to minimize the effect of withdrawal. For the purpose of evaluating Specific Aim 2, a similar methodology will be employed to estimate the time averaged difference in physical activity counts as measured by accelerometry.

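### The planned Aim 2 contrast can show whether total activity rises, but not whether the rise comes entirely from the training sessions, as Hypothesis 2 claims

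*Combined protocol and SAP*

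**What the plan says.** **Hypothesis.** Under Specific Aims and Hypotheses, Hypothesis 2 predicts for the RET arm an "increase in total physical activity by the end of the trial that is attributable entirely to an increase in RET".

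**Outcome.** Under Day 1 (Screening Day): "The primary outcome measures for Aim 2 are self-report and objectively measured estimates of total physical activity". The self-report instrument is the IPAQ. Statistical Considerations gives no analysis for it.

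**Analysis.** Statistical Considerations carries the Aim 1 model over to Aim 2: "a similar methodology will be employed to estimate the time averaged difference in physical activity counts as measured by accelerometry". It does not say which weeks enter the average.

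**Timing.** Baseline Assessment and 16-Week Trial places the on-trial monitoring in weeks 5, 10 and 16, all inside the training period. The Study Schedule gives the RET arm two 90-minute sessions in each of those weeks.

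**Wear rule.** Under Physical Activity Assessment, participants will be "asked to wear it as much as possible, unless sleeping, bathing or swimming". That sentence is written for the baseline week, and no separate rule is given for training weeks.

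**Intent.** The introductory section, before Background and Significance, considers it plausible that structured training "reduces physical activities performed during the rest of the day, and that this change in total physical activity could affect health outcomes". It also states an intention to measure activity outside the intervention, but gives no method for isolating it.

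**The concern.** Hypothesis 2 makes two claims: total activity is higher by the end of the trial, and activity outside the sessions contributes nothing to the rise. The second claim is about a component of activity, and the plan estimates only one aggregate. If the total difference is positive, the trial could report Hypothesis 2 as supported when part of the rise came from elsewhere, or when sessions added more than the total shows and activity in the rest of the week fell. The protocol gives its own reasons to care about the difference: it raises compensation as a possibility and hopes to characterise who benefits by whether extra-intervention activity is maintained.

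There is also a mismatch of timing. Hypothesis 2 refers to the end of the trial, and Summary of Experimental Design bases the primary hypotheses on baseline against end of treatment. The planned estimate averages over time.

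**Working it through.** **1. The plan's own figure.** No sample-size figure is given for Aim 2. For Aim 1 the plan states 34 per group (effect 0.6 SD, correlation 0.6, power 90%, alpha .05). For a time-averaged difference over *m* measures,

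n = 2(z_α + z_β)² × [1 + (m − 1)ρ] / (m d²).

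With one-sided alpha and m = 4 this gives 2 × (1.645 + 1.282)² × 0.70 / 0.36 = 34 after rounding up. Two-sided, m = 4 gives 41. The plan states neither *m* nor sidedness. The present point does not rest on this figure; 34 per arm is simply carried forward.

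**2. What the contrast identifies.** Let S be the between-arm difference in session activity and N the difference outside sessions, both in SD of total counts. The planned contrast estimates T = S + N.

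| S | N | T | Meaning |
|---|---|---|---|
| 0.6 | 0 | 0.6 | rise entirely from sessions |
| 0.3 | 0.3 | 0.6 | partial attribution |
| 0.9 | −0.3 | 0.6 | partial compensation |
| 0 | 0.6 | 0.6 | rise wholly outside sessions (limiting case) |

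With 34 per arm, the three on-trial weeks, ρ = 0.6 and a two-sided 5% test, the variance factor is (1 + 2 × 0.6)/3 = 0.733 and SE = √(0.733 × 2/34) = 0.208 SD. Power is Φ(0.6/0.208 − 1.96) = 82% in every row. Only the first row satisfies Hypothesis 2.

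**3. Reading the counts as session-free does not help.** If session time were excluded, in line with the stated intent, the single contrast would estimate N and could no longer show a rise in total activity. One contrast cannot carry both parts on either reading.

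**4. What it would take to support *entirely*.** The clause needs N shown to be close to zero, so a non-significant N is not enough. The plan gives no margin; 0.3 to 0.6 SD of the out-of-session measure is assumed here. The chance that the interval lies within ±margin when the true N is 0 is 2Φ(margin/SE − z) − 1, set to zero when negative. The inputs are 34 per arm and ρ = 0.6, assumed to carry over from Aim 1. Baseline adjustment multiplies the week-16 variance by 1 − 0.6² = 0.64.

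| Design | SE | 0.3 | 0.4 | 0.5 | 0.6 |
|---|---|---|---|---|---|
| Three-week average, unadjusted, 90% interval (two one-sided 5% tests) | 0.208 | 0 | 22% | 55% | 79% |
| Week 16 only, unadjusted, 90% interval | 0.243 | 0 | <1% | 32% | 59% |
| Week 16 only, baseline-adjusted, 95% interval | 0.194 | 0 | 8% | 46% | 74% |

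Using a 90% interval in the last row would raise 46% to 2Φ(0.5/0.194 − 1.645) − 1 = 65%. At a margin of 0.3 SD it would still be zero. For the first row's design, 90% power needs 64 per arm at 0.5 SD and 177 at 0.3 SD.

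**The case against.** The strongest reply is that Aim 2 concerns total daily activity, its outcomes are estimates of total activity, and the contrast estimates exactly that. This is right. A reader might infer that Aim 2 as a whole cannot be answered; the documents do not support that. The question that the introduction calls critical and unanswered is also worded around total activity. Only the attribution clause of Hypothesis 2 lacks a test.

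Two further inferences also fail. One is that full compensation and no effect both give a zero difference, and that this shows the defect. It does not: Hypothesis 2 predicts a rise, so both cases correctly fail to support it. The ambiguity that matters arises when the total is positive. The other starts from the sessions' share of worn time, about 3% (3 h out of 7 × 14 h at an assumed 14 h a day), and treats it as the size of the effect at stake. That is a share of time. Turning it into counts assumes sessions are as intense as average waking time, for which the documents give no basis.

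It is also fair that the wear rule is written for the baseline week, so inclusion of sessions in later weeks is a reading of the text, and that counts could perhaps be split afterwards. Both stand. However, no rule excludes sessions, and a split made afterwards would leave the measure and the criterion to be chosen with results in hand.

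Finally, the time-average mismatch is not specific to activity, because the same wording governs Aim 1. It is a secondary reason for the fix here.

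**Conclusion.** The point holds for one clause. The planned contrast is adequate for total activity. It cannot distinguish a positive total difference due entirely to sessions from one due partly to sessions, offset by compensation, or arising wholly outside them. This follows from T = S + N and needs no numerical assumption. The estimate also answers a time-averaged question where the hypothesis asks about the end of the trial.

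The figures for the no-change claim are illustrative. They rest on 34 analysed per arm, a correlation of 0.6 borrowed from Aim 1, a true out-of-session difference of zero, a normal approximation and assumed margins. On those terms the trial is unlikely to establish *entirely* at a tight margin and has roughly an even chance at 0.5 SD. The change is worth making because it is cheap and prevents an unsupported claim; the trial's main conclusion does not depend on it.

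**What to change.** 1. Keep total accelerometer counts as the objective Aim 2 outcome, estimated as the baseline-adjusted RET versus WLC difference at week 16.
2. Record the start and stop time of each session in the monitored weeks, and state how those times are used to separate in-session from out-of-session counts.
3. Pre-specify a second contrast, out-of-session counts per worn hour at week 16, baseline-adjusted, RET versus WLC, reported with its 95% interval.
4. State in advance the size of change that the interval must exclude before a rise is called entirely due to RET. If no margin can be justified, soften that wording in Hypothesis 2 and report the estimate and interval.

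**Cost.** Statistical text, a time log and one processing step, with no new visits or participants. The documents mention attendance tallies and total work, not clock times, so the log would be new; sessions are already scheduled and individually supervised. The split needs a monitor that stores time-stamped counts, which the documents do not specify. Using week 16 alone gives up the precision of averaging three weeks, and with 34 per arm the no-change part will probably be inconclusive. The protocol should say so beforehand.

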All participants will be initially screened by phone and asked to provide a letter from their physician approving their participation in a RET program. Primary eligibility criteria are 1) deployment to the Persian Gulf (e.g., Iraq, Kuwait, Saudi Arabia) for the purpose of Operation Desert Shield or Operation Desert Storm during the first Gulf War (1990-1992) and 2) current chronic widespread pain in multiple quadrants of the body lasting for at least 3 months. Veterans who regularly engaged in resistance exercise will not be eligible for study participation. Participants will be screened to ensure that they are not color-blind or claustrophobic, have no metal in the body and are not disabled to the point where RET would not be possible (e.g. wheel-chair bound). The Waisman Laboratory MRI center has a standard safety screen that all patients and research subjects must complete prior to entry into the 3-Tesla environment. Participants will be further screened to ensure that they are not taking any anti-convulsant or certain analgesic (e.g. opioids, muscle relaxants) medications for at least three weeks prior to the study. They will also be screened for the presence of other exclusionary criteria including explained pain conditions such as arthritis and injury, major depressive disorder with melancholic features, substance abuse or dependence (within 2 years), schizophrenia, bipolar disorder, medical or neurological disorders, peripheral neuropathy's and skin rashes on the areas that are to be pain tested.

Participants will also be assessed for the presence of FM, using American College of Rheumatology criteria (23). We will not exclude for the presence of FM, and if a significant number of GVs with unexplained pain screen positive, FM will be used as a covariate in our statistical model.

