To estimate the impact of RET on BOLD responses to pain stimuli we will use a two-sample Hotelling's T-square approach. This will test differences in the vector of means of BOLD response from pain stimuli for the control and exercise group between the baseline (before treatment) and end of the study (after treatment) for three different brain regions (anterior cingulate, insula and middle frontal cortices). These regions were chosen based on the robust brain responses observed in patients with CMP. Hotelling's T-square is a generalization of the Student's t statistic that is used in multivariate hypothesis testing. If there are q variables, the null hypothesis is that the means of variables in the first population equal the means of variables in the second population. For each subject in each group the difference between baseline value and end of the trial value for all brain regions will be computed and a Hotelling's T-square will be performed to compare the mean difference vectors for each group. With a sample size of 34 subjects we will have 80% power to detect a moderate effect size ($\sim .6$), in the treatment group, between baseline and the end of the trial.

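### Imaging is analysed as raw change scores and no baseline covariate is specified for any outcome; pre-specified baseline adjustment would gain precision from data already collected

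*Combined protocol and SAP*

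**What the plan says.** **Imaging (Statistical Considerations).** For the anterior cingulate, insula and middle frontal cortices, "For each subject in each group the difference between baseline value and end of the trial value for all brain regions will be computed". A two-sample Hotelling's T-square then compares the arms' mean difference vectors. No covariate is mentioned.

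**Symptoms and activity (same section).** "General multivariate regression models will be used to estimate the time averaged difference in pain ratings and clinical symptom scores" between the arms. The model is said to relate the response to explanatory variables and to allow for autocorrelation, but the variables are not listed. Accelerometer counts (Aim 2) are to be handled in a similar way.

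**Covariates.** The only one named in the document is fibromyalgia, under Screening and exclusion criteria: "FM will be used as a covariate in our statistical model". It enters only if enough veterans screen positive, and no threshold is given. No section names a baseline value as a covariate.

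**Sample size.** "In order to achieve 90% power, at alpha equal to .05", with a standardised effect of 0.6 and "with a correlation of .6 between measurements from each individual", "the necessary sample size would be 34 subjects per group". The plan adds: "If we take into account a 20% subject attrition rate, then the total sample size should be 41 subjects per group". The Subjects section nevertheless randomises 68 in total, 34 per group.

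**Baseline data.** Day 1 (Screening Day) includes testing on the Aim 1 primary measures. The Study Schedule has assignment follow Day 1 testing, with the baseline scan to come. The accelerometer week immediately precedes that scan, and training starts about a week after it.

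**The concern.** Under randomisation, a change score and a baseline-adjusted comparison estimate the same treatment effect, but the adjusted comparison has the smaller large-sample variance unless the baseline-to-end correlation is 1. The imaging plan therefore commits to the less efficient use of a baseline scan that every participant has anyway.

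For symptoms and activity the problem is silence. Baseline could be a covariate, a subtracted value, one of the averaged responses, or left out. These choices differ materially in power, and if the choice is left until the data are in hand it can be influenced by them. The trial has little precision to spare, because it randomises 34 per group where its own attrition allowance asks for 41. The unquantified trigger for the fibromyalgia covariate leaves a further modelling choice open.

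**Working it through.** **1. The plan's own figures.** For a time-averaged difference, n per group = 2(z_alpha + z_beta)² f / d², with f = (1 + (m − 1)rho)/m for m measurements. The plan gives d = 0.6, rho = 0.6 and 90% power. It states neither m nor sidedness.

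- m = 4: f = (1 + 1.8)/4 = 0.70. One-sided: 2 × (1.645 + 1.282)² × 0.70/0.36 = 33.3, so 34. Two-sided: 2 × (1.960 + 1.282)² × 0.70/0.36 = 40.9, so 41.
- m = 3: 35 one-sided, 43 two-sided.

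The stated 34 is matched exactly by a one-sided test with four measurements. The trial period has three post-baseline visits (weeks 6, 11 and 17), so the fourth could be baseline. The formula does not settle how baseline enters the analysis.

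The imaging statement (34 subjects, 80% power, effect about 0.6) reproduces as a one-sample Hotelling test within the treatment group: three regions, Mahalanobis distance 0.6, noncentrality 34 × 0.36 = 12.24, F(3, 31), power 79.5%.

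**2. Imaging: change score against adjustment.** With equal variances at baseline and end (set to 1), a change score has variance 2(1 − rho) and a baseline-adjusted end value 1 − rho². The ratio is (1 + rho)/2. The documents give no BOLD correlation, so rho is an assumption here.

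| rho | change score | adjusted | ratio | reduction |
|---|---|---|---|---|
| 0.3 | 1.40 | 0.91 | 0.65 | 35% |
| 0.4 | 1.20 | 0.84 | 0.70 | 30% |
| 0.6 | 0.80 | 0.64 | 0.80 | 20% |
| 0.8 | 0.40 | 0.36 | 0.90 | 10% |

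For the planned between-arm test at 34 per arm, take a distance of 0.6 on the change-score scale. Noncentrality is 17 × 0.36 = 6.12 and power is 50%. Dividing the squared distance by 0.80 gives noncentrality 7.65 and power of about 60% (70% to 55% for rho 0.3 to 0.8). This treats the three regions as having the same rho and ignores the three degrees of freedom spent on baselines.

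**3. Symptoms.** Inputs: d = 0.6, correlation 0.6 between the three post-baseline visits, 34 per arm, and two-sided 0.05 (my choice). Power = Phi(d/√(2f/34) − 1.96). With baseline-to-visit correlation rb:

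- No baseline: f = (1 + 2 × 0.6)/3 = 0.733; 0.6/0.2077 = 2.89; power 82%.
- Change from baseline, rb = 0.6: f = 0.733 + 1 − 1.2 = 0.533; power 92%.
- Adjusted, rb = 0.6: f = 0.733 − 0.36 = 0.373; power 98%.
- Adjusted, rb = 0.5: f = 0.733 − 0.25 = 0.483; power 95%.
- Adjusted, rb = 0.4: f = 0.733 − 0.16 = 0.573; power 90%.
- Adjusted, rb = 0.3: f = 0.733 − 0.09 = 0.643; power 87%.

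The change score has f = 1.733 − 2rb. It equals the no-baseline figure at rb = 0.5 and is worse below that (1.133 at rb = 0.3). Adjustment is better than no baseline at every value shown.

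**4. Baseline as one of four averaged responses.** The plan does not exclude this. A constant post-baseline effect of 0.6 is diluted to (0 + 3 × 0.6)/4 = 0.45. With f = 0.70, 0.45/√(1.40/34) = 2.22, and power is about 60%.

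**The case against.** **A reader might infer that the symptom model is unadjusted.** The documents do not say so. Explanatory variables are mentioned but not listed, the fibromyalgia sentence shows that the model can take covariates, and the Summary of Experimental Design bases the primary hypotheses on baseline compared with end of treatment. If that means change from baseline, power is already 92% at 34 per arm under the plan's correlation. Nor does the figure of 34 prove that baseline is ignored: it depends on two unstated assumptions, and a power formula does not define an analysis model.

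**A reader might attribute the 82% to omitting baseline.** Much of the gap from the plan's 90% comes from sidedness. One-sided at 0.05, the same no-baseline model with three visits and 34 per arm has 89% power.

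**A reader might quote a halving of symptom variance.** The drop from 0.733 to 0.373 is 49%, but it needs 0.6 to hold from baseline to every visit. At 0.3, 0.4 or 0.5 the reduction is 12%, 22% or 34%.

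**A reader might compute power on the 27 per arm left after 20% loss.** The plan states an intention-to-treat analysis of everyone randomised, with carry-forward and multiple imputation. Those methods raise their own questions, but the plan is not a completer analysis.

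**A reader might say that the fibromyalgia covariate is chosen on outcome data.** Its trigger is prevalence at screening. The missing threshold is the smaller fault.

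It is also fair to say that change scores use baseline and are unbiased under randomisation, so the imaging analysis is valid as written. Adjusting for cohort is optional: the Subjects section mentions blocks without a size, and participants may fall out of step with their cohort. None of this removes the efficiency gain or the need to specify the model.

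**Conclusion.** The point holds as one of efficiency and specification, not of validity. The imaging analysis is a raw change-score comparison, and baseline adjustment is specified for no outcome.

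For imaging, adjustment removes 20% of the variance at an assumed correlation of 0.6, and 35% to 10% over 0.3 to 0.8, assuming equal variance at baseline and end. For symptoms at 34 per arm and two-sided 0.05, adjustment gives 87% to 98% power for baseline-to-visit correlations of 0.3 to 0.6, against 82% with no baseline. The symptom gain over what is actually planned cannot be stated, because the planned model is not defined. The plan gives 0.6 only as a general within-person correlation, so its use from baseline to each visit is also an assumption.

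The gain does not extend to the patient global impression of change. That scale rates change directly and has no baseline value.

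**What to change.** - **Imaging:** replace the change-score Hotelling's T-square with a multivariate analysis of covariance of the three end-of-trial regional responses on their three baseline values.
- **VAS pain, SF-36 PCS and activity counts:** list the explanatory variables, include the baseline value of the same measure as a covariate, and state that baseline is not one of the averaged responses. Exempt the global impression of change.
- **Fibromyalgia status:** include it unconditionally or not at all. Cohort may be added but is not required.
- **Sample size:** state the sidedness and the number of measurements behind 34.

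**Cost.** No new data, and a few degrees of freedom: for imaging, three baselines take the error term of the F test from 64 to 61 at 34 per arm.

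One point touches conduct. The Study Schedule places the baseline scan and accelerometer week after assignment but before training, whereas a sentence under Baseline Assessment and 16-Week Trial lists baseline testing ahead of assignment. The order should be reconciled. Preferably, assignment should follow those measurements. Otherwise the plan should say that these covariates are pre-treatment, not pre-randomisation. VAS pain and PCS are measured on Day 1 before assignment, so they need only a change of wording.
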